#### **2.1.3.2 Deaths**

The death observation periods are defined below:

- Death on-treatment: deaths occurring during the treatment epoch.
- Death on-study: deaths occurring between informed consent date in this study and the end of the study.

#### **2.1.3.3 Laboratory safety parameters**

Clinical laboratory data consists of blood analysis, including hematology, clinical chemistry, and urinalysis. Clinical laboratory values will be converted into standard international units, and both US conventional units and international units will be used in all displays for continuous variables.

The following clinical laboratory test results are assessed as part of safety profile:

- Clinical chemistry: Sodium, potassium, calcium, chloride, blood urea nitrogen, creatinine, lactate dehydrogenase, total protein, albumin, glucose, phosphorus, and creatine kinase. These are scheduled for every 3 months.
- Liver function tests: ALT, AST, AP, gamma-glutamyl-transferase, total bilirubin, and direct bilirubin. These are scheduled for every 3 months.
- Hematology: Complete blood count with differential and platelet count, including hematocrit, hemoglobin, red blood cell, white blood cell, platelet, neutrophil, lymphocyte, monocyte, eosinophil, and basophil counts. These are scheduled for every 3 months.
- Coagulation studies: Prothrombin time (Protome), partial thromboplastin time, international normalized ratio, and D-dimer. These are scheduled for every 3 months.
- Urinalysis: Dipstick for glucose, protein, hemoglobin, leukocytes, ketones, and bilirubin. These are scheduled for every 3 month visit in this study.
- Safety biomarkers: hsCRP, iron, ferritin, cardiac troponin I, IL-6, IL-8, ceramide in plasma and calcitonin. These are scheduled for every 3 month visit in this study.
- Immune response assessments: anti-olipudase alfa IgG antibodies. These are scheduled for every 3 month visit in this study.

- If an IAR is anticipated to be a hypersensitivity reaction, additional laboratory parameters will be evaluated as soon as possible: tryptase activity and complementation activation, IgG and IgE. A skin testing may also be performed.
- If an IAR is anticipated to be a cytokine release syndrome (CRS), additional laboratory parameters will be evaluated as soon as possible: IL-6, IL-8, calcitonin.

#### **2.1.3.4 *Vital signs***

Vital signs are collected before and 1-hour after each infusion in this study; parameters include: heart rate, systolic and diastolic blood pressure, temperature and respiratory rate. Weight is collected before each infusion except in the case of home infusion, it is only collected in the previous site visit. Height is collected every six months of study treatment exposure for patients from DFI13803, and every 12 months into this study for patients from DFI13412.

#### **2.1.3.5 *Electrocardiogram***

ECGs are manually read by an independent expert at the site. ECG parameters, including those related to QT intervals, are evaluated by a central laboratory. ECG is conducted for every 6 months of exposure to study treatment.

ECG parameters from the central laboratory will include interpretations related to:

- Sinus, supraventricular and ventricular rhythm.
- AV and intraventricular conduction.
- Axis and voltage.
- Chamber hypertrophy and enlargement.
- ST-T abnormalities.
- Ischemia and infarction.

#### **2.1.3.6 *Echocardiogram with Doppler***

Echocardiogram with Doppler is scheduled for every 12 months (starting at 3 months in this study for pediatric patients). Examination will include, but not be limited to: ventricular cavity size, valve characterization, ejection fraction, ventricular wall thickness, regional wall motion, diastolic function, and pericardium characterization. Pulmonary blood pressure and blood flow will be determined by Doppler ultrasound.

#### **2.1.3.7 *Physical Examination***

A complete physical examination is conducted for every 6 months (starting at 3 months in this study for pediatric patients), and an abbreviated physical examination (general appearance only) is performed pre- and post-infusion at 3-month visits that do not do complete exam.

#### **2.1.3.8 *Extended Neurological Examination***

An extended neurological examination is conducted every 12 months (starting at 9 months in this study for pediatric patients).

#### **2.1.3.9 *Liver Biopsy (Patients from adult study DFI13412)***

Liver biopsy is done at screening, Week 26 and Year 3 for patients who previously participated in the DFI13412 study. Liver biopsies are evaluated by a Sanofi Genzyme pathologist for liver fibrosis grading and for sphingomyelin accumulation. Fibrosis staging will be performed using the Lathe pathology reports. Liver biopsy report will not be stored in clinical database, but be received by clinical personnel at the site and kept in the patient local study file. Data of fibrosis staging will be recorded and transferred as external data. Sphingomyelin accumulation in liver tissue that is assessed from liver biopsy will be discussed under pharmacodynamic endpoints ([Section 2.1.5](#)).

#### **2.1.3.10 *Liver ultrasound Doppler (Patients from pediatric study DFI13803)***

Liver ultrasound Doppler is performed for patients transitioning from DFI13803. Ultrasound is performed at Screening and Week 52 in the original study, then every 6 months (starting at 3 months in this study for pediatric patients) until 2 years, and yearly thereafter. This evaluation documents hepatic blood flow characteristics, principally portal vein pressure and blood flow direction. The structures to be examined include hepatic portal vein, the main hepatic artery and the main hepatic vein. Additional structures that may be examined include the network of intrahepatic portal veins, the main and intrahepatic arteries, the hepatic veins, the main and intrahepatic portal veins, the intrahepatic portion of the inferior vena cava, collateral venous pathways, and transjugular intrahepatic portosystemic shunts. Liver ultrasound Doppler will be performed using methods that are compatible with the standard institutional procedures of the investigational site.

### **2.1.4 *Efficacy endpoints***

Efficacy endpoints in this study are secondary endpoints. The schedule of data collection of these endpoints is described in the flow charts in Section 1.1 to 1.3 in the protocol.

#### **2.1.4.1 *Abdominal magnetic resonance imaging***

Spleen and liver volumes will be assessed by abdominal MRI to quantify the degree of splenomegaly and hepatomegaly at approximately every 6 months for first 2 years in this study (starting at 3 months in this study for pediatric patients); for further details of timing, please refer to the protocol. The MRIs will be collected and read centrally by a third party blinded to patient number and study visit.

The vendor will provide spleen and liver volumes in the unit of cubic millimeters. This will be converted to the standard unit of cubic centimeters for reporting purposes, by dividing by 1000. The analysis will also use the unit of Multiples of Normal (MN), and the algorithm used is as follows:

Spleen Volume (MN) = Spleen volume (cm^3) / [2\*weight (kg)]

Liver Volume (MN) = Liver volume (cm^3) / [25\*weight (kg)]

where weight is the available value closest to the MRI scan date.

#### **2.1.4.2 Pulmonary function tests**

Pulmonary function tests (PFT) will be performed in patients  $\geq 5$  years old at screening in the original study to measure lung volumes, air flow, and gas exchange for evidence of interstitial lung disease (ILD) at approximately every 6 months for first 2 years in this study (starting at 3 months in this study for pediatric patients), and every 12 months thereafter; for further details of timing, please refer to the protocol. Completion of PFTs may depend on patient age or cooperation, or both.

Pulmonary function testing will include, but will not be limited to, assessment of forced vital capacity (FVC), forced expiratory volume in the first 1 second (FEV1) of the FVC maneuver, and total lung capacity. Diffusing capacity of carbon monoxide (DLCO) will be used to measure gas exchange across the alveolocapillary membrane. Observed values of PFT parameters and DLCO will be reported. Percent predicted values will be computed based on following algorithm (height and hemoglobin values are from the available ones closest to the PFT evaluation date/time, and age is calculated at the PFT evaluation date):

Percent predicted values of FEV1 and FVC will use the Global Lung Initiative (GLI) 2012 reference equations (1).

Predicted TLC (Liters) will use the following formula for adults (2) and children (3)

Adults ( $\geq 18$  years of age):  $= 0.0795 * \text{height(cm)} + 0.0032 * \text{Age(years)} - 7.333$  for males  
 $= 0.0590 * \text{height(cm)} - 4.537$  for females

Children ( $< 18$  years of age):  $\exp(24.67 - 4.91 * \ln(\text{Height(cm)}) - 7.16 * \ln(\text{Age(months)}) + 0.059 * \text{Sex} + 1.47 * \ln(\text{Height}) * \ln(\text{Age}))$

Percent predicted TLC =  $100 * \text{Observed TLC} / \text{Predicted TLC}$

Percent predicted DLCO will be computed as follows: (2, 4) and children (3, 4):

Predicted DLCO (adults), mL CO/min/mmHg:  
 $= 0.416 * \text{Height(cm)} - 0.219 * \text{Age(years)} - 26.34$  for males  
 $= 0.256 * \text{Height(cm)} - 0.144 * \text{Age(years)} - 8.36$  for females

Predicted DLCO (children), mmol/min/kPa (Sex: 0=female, 1=male):  
 $= \exp(34.80 - 6.89 * \ln(\text{Height(cm)}) - 8.66 * \ln(\text{Age(months)}) + 0.10 * \text{Sex} + 1.79 * \ln(\text{Height}) * \ln(\text{Age}))$

Unit conversion: mL CO/min/mmHg = mmol/min/kPa \* 2.987

Hb-adjustment factor (to be applied to DLco in unit of mL CO/min/mmHg)  
=  $1.7 \times \text{Hb}(\text{g/L}) / [10.22 + \text{Hb}]$  for males, or children 15-18 yrs  
=  $1.7 \times \text{Hb}(\text{g/L}) / [9.38 + \text{Hb}]$  for females, or children <15 yrs

DLco adjusted for Hb = Observed DLco/HB-adj factor

Percent predicted (Hb-adjusted) DLco =  $100 \times \text{DLco \text{adjusted for Hb}} / \text{Predicted DLco}$

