#### **2.4.8.2 *Pulmonary function testing***

The parameters evaluated are DLco (mL/min/mmHg), FVC (L), FEV1(L), TLC (L). Since the local sites use different equations to calculate percent predicted values, the calculation is standardized internally by using the formula provided in [Section 2.1.4.2](#); the percent predicted values calculated at site will remain in the database but will neither be listed nor summarized. The observed values used in analyses are provided by local sites for original study, and will be used for calculation of percent predicted values. The patients transitioning from the pediatric study will continue to use children formula used during the original study even if the age limit prescribed for that formula is crossed during the extension phase.

For all 4 tests, percent (%) predicted values will be summarized for observed values, change from baseline and percent change from baseline using the safety population at scheduled study visit. The analysis of covariance method (including baseline as covariate) and WMW test p-values for the change from baseline and percent change from baseline will be provided in the summary tables for all 4 tests. Box plots of observed values, percent change from baseline for these 4 tests will be provided for the safety population. By-patient plots for all 4 tests over time will be provided.

Analysis of covariance will be used to explore difference among different age cohorts for patients from pediatric study DFI13803, using the following model:

Percent change in percent predicted PFT from baseline = age cohort + baseline percent predicted PFT

For patients from adult study DFI13412, a binary measure of responder (yes vs no) will be derived based on the change from baseline in % predicted DLco at each post-baseline visit. A patient is a responder at the visit, if the patient has change from baseline in % predicted DLco  $\geq 15$ . This binary measure of % predicted DLco will be included in data listing.

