#### **2.4.8.15 Subgroup analyses for efficacy (Patients from pediatric study DFI13803)**

For Patients from pediatric study DFI13803, below subgroup analyses will be performed.

To assess persistence of efficacy in patients with different baseline disease severity, the following subgroup analysis will be conducted:

- Spleen volume (MN) by baseline spleen volume severity (severe vs not severe). Severe patients is defined as baseline spleen volume  $>15$  multiple of normal (MN).
- % predicted DLco by baseline % predicted DLco severity (severe vs not severe). Severe patients is defined by baseline % predicted DLco  $<40\%$ .

To assess the impact of immunogenicity on efficacy, descriptive summaries for spleen volume and platelet count will be conducted for the following two groups of patients treated with olipudase alfa:

- Patients with treatment emergent anti-drug antibody (ADA) positive defined as either treatment induced or treatment boosted ADA positive at any time during olipudase alfa treatment.
- Patients with ADA negative defined as neither treatment induced or treatment boosted ADA positive at all time during olipudase alfa treatment.

For all the above subgroup analyses, within each subgroup, the change or percent change from baseline at each longitudinal time point will be summarized and analyzed with the analysis of covariance (ANCOVA) approach with baseline as covariate.

The efficacy measures (spleen volume and platelet count) will also be compared between manufacturing Process B, Process C (█) and Process C (█) as described below.

- To compare Process B and Process C (█), descriptive summaries for above efficacy measures will be created for the patients who started on Process C (█) only (patients never on Process B) versus patients who started on Process B and then switched to Process C (█) (Patients who were ever on Process B). In this analysis, the data when patients were exposed to Process C (█) will be excluded.
- Descriptive summaries for above efficacy measures will be created for the patients who did not switch to Process C (█) yet (patients never on Process C (█)) versus patients who switched to Process C (█) (Patients ever on Process C (█)).
- For patients who switched to Process C(█) and patients who switched to Process C (█) separately, the individual patient plot of observed values at each time point for above efficacy measures will be created with time point for start of each process (B, C (█) and C (█)) added on the plot.

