## Appendix A Potentially clinically significant abnormalities (PCSA) criteria

Measures	Adult criteria	Pediatric criteria
Liver function tests		
ALT	>3 * ULN >5 * ULN >10 * ULN >20 * ULN	Same as adult
AST	>3 * ULN >5 * ULN >10 * ULN >20 * ULN	Same as adult
Alkaline Phosphatase	>1.5 * ULN	Same as adult
Total Bilirubin	>1.5 * ULN >2 * ULN	≥1.3 ULN
ALT and Total Bilirubin	ALT >3 * ULN and Total Bilirubin >2 * ULN	Same as adult
Hematology		
WBC	<3.0 GIGA/L (non-Black), <2.0 GIGA/L (Black), ≥16.0 GIGA/L	12 years or above, but less than 18 years by age: <4.5 GIGA/L >13.5 GIGA/L 6 years or above, but less than 12 years by age: <5.0 GIGA/L >17.0 GIGA/L 2 years or above, but less than 6 years by age: <3.0 GIGA/L >16.0 GIGA/L 28 days/1 month to 23 months old <4.0 GIGA/L >20.0 GIGA/L

Measures	Adult criteria	Pediatric criteria
Lymphocytes	>4.0 GIGA/L	12 years or above, but less than 18 years by age: <0.6 GIGA/L >6.0 GIGA/L 6 years or above, but less than 12 years by age: <1.0 GIGA/L >8.0 GIGA/L 2 years or above, but less than 6 years by age: <1.0 GIGA/L >9.5 GIGA/L 28 days/1 month to 23 months old <2.0 GIGA/L >13.5 GIGA/L
Neutrophils	<1.5 GIGA/L (non-Black) <1.0 GIGA/L (Black)	2 years or above, but less than 18 years by age: <1.2 GIGA/L >1.0 ULN 28 days/1 month to 23 months old <1.0 GIGA/L (1-3 months) <1.2 GIGA/L (3-24 months) >1 ULN
Monocytes	>0.7 GIGA/L	N/A
Basophils	>0.1 GIGA/L	N/A
Eosinophils	>0.5 GIGA/L or >ULN if ULN $\geq$ 0.5 GIGA /L	Same as adult
Hemoglobin	Males: $\leq$ 115 g/L ( $\leq$ 7.14 mmol/L) and 20% decrease from baseline; $\geq$ 185 g/L ( $\geq$ 11.48 mmol/L) Females: $\leq$ 95 g/L ( $\leq$ 5.9 mmol/L) and 20% decrease from baseline; $\geq$ 165 g/L ( $\geq$ 10.24 mmol/L) Decrease from Baseline $\geq$ 20 g/L (1.24 mmol/L)	24 months/2 years to $<$ 16/18 years old: <10.0 g/dL and 20% decrease from baseline, or decrease from baseline $\geq$ 2 g/dL 28 days/1 month to 23 months old (Infants): <9.0 g/dL and 20% decrease from baseline, or decrease from baseline $\geq$ 2 g/dL
Hematocrit	Males: $\leq$ 0.37 v/v and 20% decrease from baseline; $\geq$ 0.55 v/v Females: $\leq$ 0.32 v/v and 20% decrease from baseline; $\geq$ 0.5 v/v	2 years or above, but less than 18 years by age: <0.32 l/l or 32% 28 days/1 month to 23 months old <0.29 l/l or 29% >0.42 l/l or 42%
RBC	18 years or above by age $\geq$ 6 TERA/L	N/A
Platelets	<100 GIGA/L and 20% decrease from baseline $\geq$ 700 GIGA/L	Same as adult

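### The DLco hemoglobin correction labels Hb in g/L, but its constants fit only g/dL; programmed as written, % predicted DLco comes out about 30% to 50% too low

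*SAP*

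**What the plan says.** SAP section 2.1.4.2 (Pulmonary function tests) gives two rows for the hemoglobin adjustment factor. For males and for children aged 15 to 18 it is "1.7 \times \text{Hb}(\text{g/L}) / [10.22 + \text{Hb"]. For females and for children under 15 it is "1.7 \times \text{Hb}(\text{g/L}) / [9.38 + \text{Hb"]. The factor is a divisor: "DLco adjusted for Hb = Observed DLco/HB-adj factor". The adjusted value is then expressed as a percentage of predicted DLco. The hemoglobin used is the available value nearest the test. The section spells out a unit conversion for DLco itself (a multiplier of 2.987) but none for hemoglobin.

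Section 2.4.8.2 makes this calculation the only analysed source of % predicted values, because "the percent predicted values calculated at site will remain in the database but will neither be listed nor summarized". It also derives an adult responder flag, a rise of at least 15 points in % predicted DLco, and says: "This binary measure of % predicted DLco will be included in data listing". Section 2.4.8.15 sets up a pediatric severity subgroup: "Severe patients is defined by baseline % predicted DLco" below 40%.

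Elsewhere the SAP uses both unit systems. For laboratory data in section 2.1.3.3, "both US conventional units and international units will be used in all displays for continuous variables". Appendix A gives adult hemoglobin criteria in g/L, for example "Decrease from Baseline $\geq$ 20 g/L (1.24 mmol/L"), but pediatric hemoglobin criteria in g/dL.

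**The concern.** A hemoglobin correction should do nothing at a normal hemoglobin, raise DLco in an anemic patient and lower it when hemoglobin is high. With Hb in g/L these rows cannot behave that way, because the factor stays well above 1 at any hemoglobin a patient could have. Every DLco would be adjusted down, including in anemia.

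Three things are at stake if the formula is programmed literally. Levels and absolute changes in % predicted DLco, part of a secondary efficacy endpoint, would be compressed. The pediatric severity subgroup would take in patients who are not severe by the SAP's own 40% definition. And the correction would respond very little to a change in hemoglobin, so a DLco change caused by hemoglobin alone would pass into the result. The last matters here because hemoglobin is itself an efficacy parameter in this trial (protocol section 9.2.4, SAP section 2.4.8.7).

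**Working it through.** **Inputs.** Constants c = 10.22 and c = 9.38, the g/L label and the division of observed DLco by the factor come from SAP 2.1.4.2. The scale of hemoglobin comes from Appendix A: adult male limits 115 and 185 g/L, adult female limits 95 and 165 g/L, pediatric limits 10.0 g/dL (9.0 g/dL in infants). The SAP gives no worked value of the factor to reproduce.

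**Where the factor is neutral.** With f(h) = 1.7h/(c + h), setting f = 1 gives h = c/0.7.
- c = 10.22: h = 14.6
- c = 9.38: h = 13.4

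In g/dL both lie inside the Appendix A adult range (9.5 to 18.5 g/dL). In g/L both are far below every hemoglobin limit in Appendix A. The constants therefore need g/dL, and this follows from the SAP alone.

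**Size of the error if g/L is used.** For a true hemoglobin of x g/dL, the ratio of reported to correct adjusted DLco is f(x)/f(10x) = (c + 10x)/[10(c + x)].

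| Hb (g/L) | c | Factor, g/L as written | Factor, g/dL | Reported/correct |
|---|---|---|---|---|
| 80 | 10.22 | 1.507 | 0.746 | 0.495 |
| 100 | 10.22 | 1.542 | 0.841 | 0.545 |
| 120 | 9.38 | 1.577 | 0.954 | 0.605 |
| 140 | 10.22 | 1.584 | 0.983 | 0.620 |
| 165 | 9.38 | 1.609 | 1.084 | 0.674 |
| 185 | 9.38 | 1.618 | 1.128 | 0.697 |

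Over an assumed range of 80 to 185 g/L in both rows, the ratio runs from 0.495 to 0.697. Kept to each sex's own Appendix A adult limits, it is 0.577 to 0.680 for males and 0.553 to 0.674 for females.

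**Effect on the cut-points, for Hb assumed between 100 and 165 g/L.**
- Severity cut: a reported 40% corresponds to a correct 40/0.545 = 73.4% down to 40/0.656 = 61.0% (c = 10.22), and 40/0.564 = 70.9% down to 40/0.674 = 59.4% (c = 9.38).
- A patient truly at 50% is reported at 50 × 0.545 = 27.3% up to 50 × 0.674 = 33.7%, and so is classed as severe.
- Adult responder flag at stable Hb: a reported 15 points needs 15/0.545 = 27.5 down to 15/0.674 = 22.3 true points.

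**Loss of the correction.** The documents give no expected hemoglobin change, so the rises below are assumptions. The table shows the fall in adjusted DLco for a fixed observed DLco, as a range across the two rows.

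| Assumed Hb rise (g/L) | Hb in g/dL | Hb in g/L, as written |
|---|---|---|
| 100 to 110 | 4.4% to 4.6% | 0.8% |
| 110 to 130 | 7.1% to 7.4% | 1.2% to 1.3% |
| 100 to 130 | 11.2% to 11.7% | 2.0% to 2.1% |

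If the lung is unchanged and observed DLco rises only as the correct formula predicts, the 110 to 130 g/L case leaves a spurious gain. It is (1 − 0.0131)/(1 − 0.0741) = 1.066, or 6.6%, with c = 10.22, and 6.3% with c = 9.38.

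**The case against.** The strongest reply is that the numerical harm depends on a program nobody has seen. The SAP cites a published standard for the DLco computation, so the programmer may have worked from that. Conventional units are available alongside international ones, and about 20 of the 25 expected patients are pediatric, the group for which Appendix A uses g/dL. A factor near 1.6 for every patient might also be noticed in the by-patient plots. All this is fair, and it is why the size of the error is stated conditionally. It does not make the written rule right. Section 2.1.3.3 converts laboratory values to international units, and the formula's own label confirms g/L. If g/dL was used, the program departs from the SAP text.

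A second reply is that the missing letter may be a fault in converting the PDF to text. This cannot be fully excluded, and a look at the printed page settles it. It is unlikely, because the label is the same in both rows and g/dL is rendered correctly in Appendix A.

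A third reply concerns weight. The primary objective is safety, DLco is one of four lung function tests within a secondary endpoint, and no decision rule depends on it. The responder flag is only listed, for five adults. Percent change and p-values are less affected, since a near-constant scale factor cancels when hemoglobin is stable. These points stand. They limit the damage but leave the levels, the absolute changes, the severity subgroup and the lost hemoglobin correction.

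Finally, the range 0.50 to 0.70 uses an assumed lower hemoglobin of 80 g/L and applies 185 g/L to both rows. Within the Appendix A adult limits it narrows to about 0.55 to 0.68. The conclusion is the same on either range.

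**Conclusion.** The concern holds. Both rows of the adjustment carry the wrong unit for their constants, and nothing in the SAP converts hemoglobin before it is used. Followed faithfully, the plan gives Hb-adjusted % predicted DLco at 0.50 to 0.70 of its correct value for hemoglobin of 80 to 185 g/L. It shifts the pediatric 40% severity cut to 59% to 73% for hemoglobin of 100 to 165 g/L, and it removes most of the hemoglobin correction. That the constants need g/dL is certain from the SAP's own figures. Whether any result is wrong depends on the unit actually programmed, and the spurious-gain figures also rest on assumed hemoglobin rises. Because this formula is the only analysed source of the endpoint, the text must be corrected and the program checked before the DLco results are relied on.

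**What to change.** Change the label to g/dL in both rows of SAP section 2.1.4.2. Alternatively, keep Hb in g/L and replace the constants with 102.2 and 93.8. The two are identical: at 140 g/L the second form gives 238/242.2 = 0.983 and 238/233.8 = 1.018, the same as with 14.0 g/dL and the present constants.

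Then confirm which unit the analysis program feeds into the formula, for adults and for children. If it was g/dL, only the text changes. If it was g/L, re-derive baseline and post-baseline Hb-adjusted % predicted DLco, the pediatric severity subgroup and the listed adult responder flag, and re-run the summaries and models that use them.

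The cost is a one-line correction and a program check, with a re-run only in the second case. No new data are needed.
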